## 13.3. Analysis Population

The intent-to-treat (ITT) population will consist of all enrolled subjects in the study who have undergone tonsillectomy and had contact with the BiZact™ device. The endpoint analyses based on the ITT population will be considered the principal analyses.

The per-protocol (PP) population will consist of all patients in the ITT population who do not have a major protocol violation. Analyses on the PP population will provide supporting evidence to the primary results.

## 13.4. Statistical Analysis Endpoints

### 13.4.1. Primary Endpoint

The primary hypotheses of this study are:

H0: Mean intra-operative blood loss =31 mL HA: Mean intra-operative blood loss < 31 mL

The analysis technique will be a 1-sample t-test, with a one-sided type I error rate ( $\alpha$ ) of 0.025. If intraoperative blood loss data appear to be non-normally distributed (as evidenced by p < 0.05 from a Shapiro-Wilk test), a Wilcoxon signed rank test will also be conducted.

The performance goal of 31 mL derives from a meta-analysis comparing modern technology-assisted to conventional tonsillectomy (i.e. electrocautery and cold steel) (7). This paper included a total of 3,139 patients included in thirty-three published studies. The values from the studies that reported intra-operative bleeding were combined to calculate a mean blood loss. This value encompasses a variety of techniques and technologies and a number of different studies to capture a realistic value for comparison.

Intra-operative blood loss during tonsillectomy with BiZact™ is expected to be low. The expected mean value for the BiZact™ device is a conservative estimate derived from data for LigaSure™ and other vessel sealing systems in the Alexiou meta-analysis (7). The expected standard deviation is the average of the standard deviation values for all studies that reported blood loss in the meta-analysis.

Expected mean intra-operative blood loss for BiZact™: 10 mL Expected standard deviation: 15.1 mL

Additionally, descriptive statistics for blood loss will be reported for different age groups (ages 2-5 and ages 6-12) as well as for different sites, surgeons, and countries.

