## 13.2. Sample Size Determination

The analysis technique will be a 1-sample t-test (or Wilcoxon ranked sign if nonparametric test is desired), with a one-sided type I error rate ( $\alpha$ ) of 0.025. A sample size of 60 subjects is selected to ensure that multiple surgeons participate and to create an opportunity for a range of subject ages to be enrolled. Statistical power for a sample size of 60 subjects exceeds 99%.

MDT17024BZP

Version 5.0 (18 MAR 2019)

Page 38 of 47

Medtronic

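### The plan leaves open whether a Wilcoxon test can decide success on a hypothesis about the mean; with right-skewed blood loss that route can run at two to six times the stated 0.025.

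*Combined protocol and SAP*

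**What the plan says.** Section 13.4.1 sets the hypotheses as "H0: Mean intra-operative blood loss =31 mL HA: Mean intra-operative blood loss < 31 mL". It then says "The analysis technique will be a 1-sample t-test, with a one-sided type I error rate" of 0.025. If blood loss "data appear to be non-normally distributed (as evidenced by p < 0.05 from a Shapiro-Wilk test"), a Wilcoxon signed rank test is run in addition. The section does not say which result counts if the two disagree.

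Section 13.2 describes the same analysis differently. After naming the t-test it adds, in parentheses, "or Wilcoxon ranked sign if nonparametric test is desired". The Statistics part of the synopsis has the same parenthesis. Neither place says who decides, when, or on what grounds.

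The planning figures in Section 13.4.1 are "Expected mean intra-operative blood loss for BiZact™: 10 mL Expected standard deviation: 15.1 mL". On the second figure the section explains: "The expected standard deviation is the average of the standard deviation values for all studies that reported blood loss in the meta-analysis". Section 13.2 concludes: "Statistical power for a sample size of 60 subjects exceeds 99" per cent.

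**The concern.** The study has one arm and one confirmatory test, and its data are to go to the FDA for a pediatric indication. The stated one-sided 0.025 is the statistical protection on its only success criterion.

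Blood loss cannot be negative and is plausibly right-skewed. For a skewed variable the mean lies above the centre that the signed rank test examines. That test can therefore reject at 31 mL when the mean is exactly 31 mL, simply because most patients bleed less than the mean. Its null hypothesis is symmetry about 31 mL, which is not the hypothesis in Section 13.4.1.

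Skewness is also what makes the Shapiro-Wilk trigger likely to fire. The Wilcoxon test would then tend to be brought in exactly where it is least suited to a claim about a mean.

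**Working it through.** **Inputs from the documents.** Performance goal 31 mL, one-sided alpha 0.025, expected mean 10 mL, SD 15.1 mL (all Section 13.4.1); n = 60 (Section 13.2).

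**Assumptions.** The documents give no distribution shape. The shapes below (normal, Weibull, gamma, lognormal) are assumptions, each set to mean 31 mL and SD 15.1 mL.

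**1. The plan's power figure.** Standard error = 15.1/√60 = 1.949. Noncentrality = (31 − 10)/1.949 = 10.77. Exact one-sample t power with 59 degrees of freedom is above 0.9999. The stated figure of more than 99% reproduces, and 0.99 is already passed at n = 12 (0.9919).

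**2. Is skew plausible?** At the planning values, a normal distribution would put Φ(−10/15.1) = 25% of patients below zero, so the expected distribution is not normal. At the null mean the case is weaker: 31/15.1 = 2.05, so zero lies about two SDs below the mean. Skew there is plausible but not forced. The coefficient of variation at the null is 15.1/31 = 0.487. This gives skewness 2 × 0.487 = 0.97 for a gamma and 3 × 0.487 + 0.487³ = 1.58 for a lognormal. The matching Weibull has skewness 0.53.

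**3. Why the Wilcoxon test misses the mean.** For the lognormal, median = 31/√(1 + 0.487²) = 27.9 mL. The mean is exactly at the performance goal, yet more than half of patients fall below it.

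**4. Rejection rates when the true mean is 31 mL** (simulation, SD 15.1 mL, n = 60, lower tail, nominal 2.5%):

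| Assumed shape | t-test | Wilcoxon signed rank |
|---|---|---|
| Normal | 2.5% | not at issue (symmetric) |
| Weibull | 3.1% | about 5% |
| Gamma | 3.7% | about 10% |
| Lognormal | 4.4% | about 15% |

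Separate runs of 4,000 samples gave 9% to 10% for the gamma and 14% to 15% for the lognormal under the Wilcoxon test. The simulation margin at 10% is 1.96 × √(0.10 × 0.90/4000) = 0.9 percentage points. Relative to 2.5%, the Wilcoxon rates are 5/2.5 = 2 to 15/2.5 = 6 times nominal. The Shapiro-Wilk trigger fired in at least 77% of the gamma and lognormal samples.

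**5. Analytic check on the t-test.** To first order, lower-tail error ≈ 0.025 + skewness/(6√n) × (2c² + 1) × φ(c), with c = 2.001. At skewness 1 this is 0.025 + 0.02152 × 9.01 × 0.0539 = 0.035, in line with the gamma result of 0.037.

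**6. What the t-test excess means in millilitres.** With sample SD 15.1 mL, the largest passing mean is 31 − 2.001 × 1.949 = 27.1 mL. Using the simulated 2.5% points of the t statistic that restore the stated level, it becomes 31 − 2.212 × 1.949 = 26.7 mL (gamma) or 31 − 2.346 × 1.949 = 26.4 mL (lognormal). The shift is 0.4 to 0.7 mL.

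**7. At the expected mean.** With mean 10 mL and SD 15.1 mL, simulated power under gamma or lognormal is at least 0.9995 for the t-test and 1.0000 for the Wilcoxon test. Both lead to the same conclusion.

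**The case against.** The strongest reply is that Section 13.4.1 already settles the matter: it names the t-test, and the Wilcoxon test is only added beside it. That is a fair reading of that section alone. It does not survive Section 13.2 and the synopsis, which offer the Wilcoxon test as an alternative at someone's discretion. Nor does Section 13.4.1 say what happens if the two results differ. Section 13.8 refers to a SAP for full details on the planned analysis. No separate SAP text is in the combined file, so a precedence rule may exist there. If so, the protocol should be brought into line with it.

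A second reply is that the consequence is small. That stands in part. The inflation matters only if the true mean is near 31 mL, about three times the expected value.

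A reader might infer something stronger: that the t-test itself is invalid and makes success too easy. The documents do not support this. Simulated t-test error of 7% to 10% at n = 60 requires the ratio 15.1/10 = 1.51 to carry over to the null, which means an SD of 1.51 × 31 = 46.8 mL. That SD appears nowhere in the plan and is 46.8/15.1 = 3.1 times the stated one. The ratio also pairs a mean taken from vessel-sealing data with an SD averaged over every study that reported blood loss, so it does not describe one distribution.

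Nor is there a clear case for replacing the t-test with a bootstrap-t as the primary test. In simulation that method still gave about 3% at SD 15.1 mL and 2.6% to 5.8% when the SD was 1.0 to 1.51 times the mean. Its power fell to about 96% at the planned effect under a lognormal.

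**Conclusion.** The concern holds for the Wilcoxon route. As written, the plan allows, or does not exclude, declaring success on a mean hypothesis from a test that does not address the mean. At the plan's own SD and sample size, that route rejects a true mean of 31 mL in about 5% to 15% of samples under the three right-skewed shapes tried, against 2.5% stated.

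The t-test is a minor matter by comparison: about 3.1% to 4.4% under the same shapes, and exactly nominal if the data are normal.

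The sizes rest on assumed shapes at a mean of 31 mL, for which the documents give no skewness. That the Wilcoxon test does not test the mean, and that the plan does not name the deciding test, rest on no such assumption.

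**What to change.** In the synopsis, Section 13.2 and Section 13.4.1:

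- Delete the option to use the Wilcoxon test instead of the t-test.
- State that the one-sample t-test alone decides success. Equivalently, the one-sided 97.5% upper confidence limit for the mean must lie below 31 mL.
- State that any Wilcoxon result is descriptive and cannot support a claim about the mean.
- Pre-specify a skew-robust analysis of the mean as a sensitivity analysis when Shapiro-Wilk p < 0.05, for example a bootstrap-t upper limit with a fixed seed.

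The cost is protocol and SAP wording, a little extra analysis, and the loss of the option to switch tests. The primary test is unchanged, so its power at the planned effect stays above 99%.

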	procedures including tonsillectomy	
	Therapeutic Goods Administration (TGA) License for ENT	
	procedures including tonsillectomy in adults, children and	
	adolescents.	
Primary Objective(s)	The primary objective of this study is to assess safety and	
	performance with the use of the BiZact™ device in children (ages 2-	
	12 at the time of the procedure, inclusive) tonsillectomy procedures.	
Study Design	A prospective, multi-center, single arm, study of BiZact™ on children	
	undergoing tonsillectomy.	
Primary Endpoint(s)	Intra-operative blood loss: The study will be considered a success if	
	the mean intra-operative blood loss is less than the mean intra-	
	operative blood loss associated with conventional tonsillectomy in a	
	large meta-analysis (Alexiou et al. 2011). See the Statistics section	
	below for more details.	

MDT17024BZP Version 5.0 (18 MAR 2019) Page 9 of 47

Medtronic

Secondary Endpoint(s)	Study will analyze and describe device performance and patient		
	response related to the following:		
	
 
Ability to dissect tonsils with investigational medical device
 
		
	via Likert Scale (Very Good, Good, Acceptable, Poor, Very		
	Poor)		
	
 
Usability Challenges
 
		
	
 
Ability to achieve hemostasis (arrest of bleeding, as
 
		
	assessed by visual inspection of the Investigator) without		
	the use of other interventions (e.g. energy device or		
	sutures)		
	
 
Evaluation of post-operative pain incidence and severity
 
		
	measured using the Wong-Baker FACES® Pain Rating Scale		
	and FLACC behavioral pain assessment scale		
	
 
Analgesic consumption (standard of care) and concomitant
 
		
	medications (via patient diary)		
Sample Size	A minimum of sixty (60) completed procedures, with at least 40%		
	study wide in the age range of 2-5 years of age, will be undertaken at		
	a minimum of 2 sites in US. When 36 procedures with subjects ≥6		
	years of age have been completed (60% of total minimum		
	enrollment), enrollment for this age group will close.		
	Power considerations are detailed in the Statistics section below.		
Inclusion/Exclusion Criteria	Inclusion Criteria:		
	1. Children subjects 2-12 years of age at time of procedure,		
	inclusive		
	Scheduled to undergo tonsillectomy		
	3. The subject and subject's Legally Authorized Representative		
	(LAR) is willing to participate and consents to participate, as		
	documented by signed informed consent form and/ or assent		

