#### **Statistics**

The analysis technique will be a 1-sample t-test (or Wilcoxon ranked sign if nonparametric test is desired), with a one-sided type I error rate ( $\alpha$ ) of 0.025. A sample size of 60 is selected to ensure that multiple surgeons participate and to create an opportunity for a range of subject ages to be enrolled. Statistical power for a sample size of 60 exceeds 99%.

The primary hypotheses of this study are:

H0: Mean intra-operative blood loss = 31 mL HA: Mean intra-operative blood loss < 31 mL

The performance goal of 31 mL derives from a meta-analysis comparing modern technology to conventional techniques (i.e. electrocautery and cold steel) (Alexiou *et al.* 2011). This paper included a total of 3139 patients included in thirty-three published studies. The values from all of the studies that reported intra-operative bleeding were combined to calculate a mean blood loss. This value encompasses a variety of techniques and technologies and a number of different studies to capture a realistic value for comparison.

Intraoperative blood loss during tonsillectomy with BiZact™ is expected to be low. The expected mean value for the BiZact™ device is a conservative estimate derived from data for LigaSure™ and other vessel sealing systems in the Alexiou meta-analysis. The expected standard deviation is the average of the standard deviation values for all studies that reported blood loss in the meta-analysis.

Expected mean for BiZact™: 10 mL Expected standard deviation: 15.1 mL

Additionally, descriptive statistics for blood loss will be reported for different age groups (ages 2-5 and ages 6-12) as well as for different sites, surgeons, and countries.

Secondary endpoints will be evaluated with descriptive statistics. For continuous variables, the mean, median, and standard deviation will be reported, along with a 95% confidence interval for the mean where appropriate.

For categorical data, proportions will be reported, along with 95% confidence intervals where appropriate.

MDT17024BZP Version 5.0 (18 MAR 2019)

Page 13 of 47

Medtronic

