#### 4.2. Purpose

The purpose of this study is to assess safety and performance of the BiZact™ device in tonsillectomy procedures in children. Sixty (60) pediatric subjects (ages 2-12 inclusive) will be treated for tonsillectomy with BiZact™ enrolled at a minimum of 2 clinical sites across the USA with enrollment and completion of the tonsillectomy procedure with the study device not to exceed 36 subjects per site. The study will be considered a success if the mean intra-operative blood loss is less than the mean intra-operative blood loss associated with conventional tonsillectomy in a large meta-analysis (7). At the conclusion of the study, data will be submitted to the FDA for consideration for a pediatric indication and for publication.

MDT17024BZP

Version 5.0 (18 MAR 2019)

Page 14 of 47

Medtronic

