#### 5.2. Endpoints

#### 5.2.1. Primary Endpoint

The primary endpoint of this study is the amount of intra-operative blood loss. The study will be considered a success if the mean intra-operative blood loss is less than the mean intra-operative blood loss associated with conventional tonsillectomy in a large meta-analysis (7). See the Statistical Design and Methods (Section 13) for additional details.

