#### 10.2.Potential Benefits

The potential benefits associated with BiZact™ device usage include, but are not limited to: reduction in pain, blood loss, time to return to normal diet, and activity post tonsillectomy procedure as compared to conventional tonsillectomy; however, there may be no benefits at all.

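### Is the 31 mL performance goal really the conventional-tonsillectomy mean that the success criterion names?

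*Combined protocol and SAP*

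**What the plan says.** The success criterion appears in the synopsis (Primary Endpoint row), Section 4.2 and Section 5.2.1. In 5.2.1 the study succeeds if mean blood loss "is less than the mean intra-operative blood loss associated with conventional tonsillectomy in a large meta-analysis". None of the three places gives a number. Section 5.2.1 then directs the reader onward: "See the Statistical Design and Methods (Section 13) for additional details". The synopsis row has a similar pointer to its Statistics section. Only Section 4.2, a statement of purpose, has none.

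The synopsis Statistics section and Section 13.4.1 set the null value at 31 mL, with the alternative that the mean is lower. They use a one-sample t-test at one-sided 0.025 and call 31 mL the performance goal. The source is a meta-analysis of modern against conventional techniques, where conventional means electrocautery and cold steel. On how the value was formed, the synopsis says: "The values from all of the studies that reported intra-operative bleeding were combined to calculate a mean blood loss". Section 13.4.1 says nearly the same and adds: "This value encompasses a variety of techniques and technologies and a number of different studies to capture a realistic value for comparison".

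The planning values are a device mean of 10 mL, taken from vessel-sealing data in the same meta-analysis, and an SD of 15.1 mL, averaged over its studies that reported blood loss.

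**The concern.** In a single-arm study the performance goal is the whole comparison. The success sentence promises a comparison with conventional technique. The description of the number mentions both techniques and technologies, and says values were combined across the studies that reported bleeding. Because the source paper compares modern with conventional methods, each such study could contribute one arm of each kind. On that reading, 31 mL is a blend and not the conventional mean.

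The text does not settle the matter. It lists no arms, arm sizes or weights, and its only counts (3,139 patients, 33 studies) describe the whole paper, not the subset that reported bleeding.

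At stake is what a positive result would mean. If the true conventional mean were below 31 mL, a device no better than conventional technique could pass more often than the nominal 2.5%. The study is a pre-market pivotal study whose data go to the FDA in support of a pediatric indication, so the question is worth asking.

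**Working it through.** **Inputs.** From Section 13.4.1: goal 31 mL, expected mean 10 mL, SD 15.1 mL, one-sided alpha 0.025. From Section 13.2: n = 60, power above 99%. The documents give no arm-level means or weights, so those used in steps 3 and 4 are assumptions.

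**1. The plan's own figure.** SE = 15.1/√60 = 1.949 mL. Noncentrality = (31 − 10)/1.949 = 10.77 on 59 degrees of freedom. Power from the noncentral t distribution is about 1.000, so the stated figure reproduces. Power at n = 60 remains at least 99% for any goal of about 18.5 mL or more.

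**2. Where the decision falls.** t(0.975, 59) = 2.001, so the margin is 2.001 × 1.949 = 3.90 mL.
- Largest observed mean that passes at this SD: 31 − 3.90 = 27.1 mL.
- Upper limit at an observed mean of 10 mL: 10 + 3.90 = 13.9 mL.

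**3. If 31 mL is a blend.** Let w be the weight of the modern arms, M their mean and C the conventional mean. Then 31 = wM + (1 − w)C, so C = (31 − wM)/(1 − w).

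| Modern mean M (assumed) | C at w = 0.4 | C at w = 0.5 | C at w = 0.6 |
|---|---|---|---|
| 10 mL | 45 | 52 | 62.5 |
| 25 mL | 35 | 37 | 40 |
| 31 mL | 31 | 31 | 31 |
| 40 mL | 25 | 22 | 17.5 |

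Whenever M is below 31 mL, C is above it. The test is then harder to pass than the stated criterion requires, and rejecting at 31 mL supports the claim against conventional technique.

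**4. The unfavourable case.** C falls below 31 mL only if M exceeds 31 mL. The chance that a device with mean exactly C passes the 31 mL test (SD 15.1, n = 60) is:

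| True conventional mean C | Chance of passing |
|---|---|
| 31 mL | 2.5% |
| 30 mL | 7% |
| 28 mL | 33% |
| 25 mL | 86% |

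The modern mean needed to produce such a C is M = (31 − (1 − w)C)/w. At w = 0.5, C = 28 needs M = 62 − 28 = 34 mL, and C = 25 needs M = 62 − 25 = 37 mL. For a just-passing observed mean of 27.1 mL to lie above C, M must exceed 36.9, 34.9 or 33.6 mL at w = 0.4, 0.5 or 0.6.

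**5. If 31 mL is conventional-only.** The number and the claim agree. The reference to variety then describes electrocautery and cold steel across several studies.

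**The case for a change.** The strongest case for acting is that a reader should be able to confirm from the protocol that beating 31 mL means beating conventional technique, and cannot. The word technologies, and the synopsis phrase about all the reporting studies, make pooling of both sides a natural reading. The false-success figures in step 4 are large if the direction is wrong. The remedy would be cheap, since the sponsor has already done the calculation. One further point favours this side: the planned 10 mL describes vessel sealers only, so it does not bound the average of all modern arms.

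What stands is that the text never says which arms gave 31 mL, and that its wording fits awkwardly with the success sentences.

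The rest is weaker:
- The criterion is not undefined. The synopsis row and Section 5.2.1 both point to the text that fixes 31 mL, and no competing number appears anywhere.
- Saying which studies were combined does not say which arms were used. Read with the success sentences, a conventional-only value is at least as tenable as a blend.
- Section 10.2 adds little. It lists as a potential benefit "reduction in pain, blood loss, time to return to normal diet, and activity post tonsillectomy procedure as compared to conventional tonsillectomy", then says there may be no benefit at all. That is not a claim the trial has undertaken to prove.
- The unfavourable case needs modern arms that bled more than conventional ones. The documents contain no figure to that effect, and the one class they do quantify is put at 10 mL.
- The source paper is fully cited, and Sections 13.1 and 13.8 refer to a statistical analysis plan. The protocol text does not show the derivation, but that does not establish that none was recorded.

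**Conclusion.** No change to the plan is needed. The gap is one of traceability: the protocol does not say which arms produced 31 mL. Filling it would leave the threshold, test, alpha, sample size and power as they are.

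Both likely readings leave the success claim sound. A conventional-only value matches it. A blend with lower-bleeding modern arms makes it conservative, with an implied conventional mean of 35 to 62.5 mL for modern means of 10 to 25 mL and modern weights of 0.4 to 0.6. At the planned performance the upper limit of 13.9 mL lies 17.1 mL below the goal (31 − 13.9), so the choice of reading would not alter the expected result.

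This rests on the plan's mean and SD, on assumed weights and modern-arm means, and on the absence of any document figure showing that modern arms bled more. Anyone reporting the trial can say in a sentence where 31 mL came from when interpreting the result; the analysis does not depend on it.
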